## **DATA COLLECTION**

KDHRC will collect quantitative data from up to 120 CHWs (60 CHWs per group) through online surveys only. If KDHRC encounters low recruitment numbers and/or high attrition rates, then KDHRC will contract with additional CBOs and utilize additional recruitment methods (e.g., social media) to reach additional participants. This will not impact the rights of or risk to study participants.

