**Guardians Receiving Information through Navigators (GRIN)**  
**Statistical analysis plan**  
**NCT05511935**  
**September, 4 2020**

## GRIN Phase I feasibility study

### Statistical design and power

#### Number of subjects

We will enroll 60 participants per group, for a total of 120 participants.

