#### Power estimate and effect size

We computed power for multiple regression based on the designated outcomes, a single measure of treatment exposure, dosage of the exposure, and demographics modeled as control measures. Table 1 shows the results of simulation models for continuous outcomes, which varied the values of  $R^2$  for the multivariate regression, the treatment measure's contribution to  $R^2$ , and the total number of predictors in the model.

We estimated power at .80, assuming each outcome measure will have the same range of explained variance, and produced a range of sample sizes under the following conditions:

- The probability of the outcome (target achieved) for the treated under the null hypothesis ( $p_1$ ) and under the alternative hypothesis ( $p_2$ ), with  $p_1 + p_2 = 1$ . Three pairs of probabilities will be used, with the constraint that  $p_1 < p_2$ .
- $R^2$  other than X, that is, the proportion of variance explained by predictors other than the treatment (the same values set for multiple linear regression were used).
- The distribution and  $\pi$  parameter of the treatment variable: binomial and the parameter 0.5 (same probability of being a case or a control).

Because varying the number of predictors had little influence on the simulation, we used six predictors with multiple linear regression. As Table 2 shows, increasing the effect size reduces the required sample size. Power for dichotomous outcomes using multivariate logistic regression required slightly larger sample sizes.

Therefore, with a medium  $R^2$  value (.30) and contribution of treatment <.30, the estimated sample size for power = 0.80 is 36 (range 23-59). Our planned sample size of 60 participants per condition will give us adequate power and allow for attrition.

Table 1. Power estimates for continuous outcomes				
$R^2$	Contribution of treatment to $R^2$	Estimated effect size	Estimated sample size for power = 0.80	Range of est. sample size for power = 0.60-0.95
0.30	0.02	0.071	112	74-184
0.30	0.05	0.200	42	28-68
0.30	0.10	0.500	19	14-29
0.40	0.02	0.053	152	96-249
0.40	0.05	0.143	58	37-94
0.40	0.10	0.333	27	18-42
0.50	0.02	0.042	191	120-314
0.50	0.05	0.111	73	47-119
0.50	0.10	0.250	34	23-55

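### The SAP's concluding sample size of 36 (23 to 59) matches no row of its own Table 1, and its stated condition names no effect that 120 participants are meant to detect

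*SAP*

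**What the plan says.** The SAP sets enrolment under Number of subjects: "We will enroll 60 participants per group, for a total of 120 participants". Under Power estimate and effect size it describes two calculations. One is for continuous outcomes, where "we used six predictors with multiple linear regression". The other is for dichotomous outcomes by logistic regression, defined by pairs of outcome probabilities p1 and p2, the R² of the other predictors, and a binomial treatment variable with parameter 0.5. Of the second it reports: "Power for dichotomous outcomes using multivariate logistic regression required slightly larger sample sizes". It also cites a second table ("As Table 2 shows, increasing the effect size reduces the required sample size"), which is not in the text available.

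The conclusion is that, at R² = .30 and "contribution of treatment <.30, the estimated sample size for power = 0.80 is 36 (range 23-59"). The next sentence reads: "Our planned sample size of 60 participants per condition will give us adequate power and allow for attrition". No attrition rate, alpha or sidedness is stated, and the text does not say whether 36 is a total or a per-arm number.

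The table headed "Table 1. Power estimates for continuous outcomes" crosses R² of .30, .40 and .50 with treatment contributions of .02, .05 and .10. The Protocol's Data collection section adds: "If KDHRC encounters low recruitment numbers and/or high attrition rates, then KDHRC will contract with additional CBOs".

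**The concern.** The concluding sentence is the only basis given for calling 120 adequate, and it disagrees with the table beside it. It borrows Table 1's terms (R² and treatment's contribution to it), yet its figure is in none of the nine rows. The bound of .30 excludes no tabulated contribution. Fixing R² = .30 still leaves three rows running from 19 to 112, so no planning effect is identified.

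What is at stake is the attrition margin. Set against 120, a requirement of 36 in total would allow (120 − 36)/120 = 70% to be lost. If 36 is per arm, the margin is (120 − 72)/120 = 40%. If Table 1's effect sizes are themselves too large for the R² they are labelled with, the true margin is far smaller, and the smallest tabulated effect is out of reach.

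**Working it through.** **Inputs.** From the SAP: power .80 (ranges for .60 to .95), six predictors, the nine rows of Table 1, and 120 participants at 1:1. Assumed: two-sided alpha .05. The SAP states none, but this value reproduces Table 1; one-sided .05 does not (89, 33 and 15 at R² = .30).

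**Method.** Noncentral F test of one predictor among six: 1 and N − 7 degrees of freedom, noncentrality f² × N. Below, c is treatment's contribution to R².

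**Step 1: reproduce Table 1.** The printed effect sizes equal c/(R² − c): .02/.28 = .071, .05/.25 = .200, .10/.20 = .500. With these, all nine printed sample sizes reproduce exactly, as totals across both arms: 112, 42, 19; 152, 58, 27; 191, 73, 34. Of the 18 range endpoints 17 match; the exception is the lower end of the first row (74 printed, 71 computed).

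**Step 2: look for 36 (23 to 59).**
- No row has it. The nearest is 34 (23 to 55), at R² = .50 and c = .10.
- In the six-predictor linear model, any f² that gives 36 has a range of 24 to 57 or 58, not 23 to 59.
- By Table 1's own formula at R² = .30, 36 needs c of about .057, a value the SAP does not use.
- A Wald logistic formula, N = (z₁₋α/₂ + z₁₋β)² × [1/(.5·p1(1 − p1)) + 1/(.5·p2(1 − p2))] / [(ln OR)² × (1 − R²other)], with R²other = .30 and an assumed p1/p2 of .20/.80, gives 7.849 × 25 / (7.687 × .70) = 36.5, range 22.8 to 60.4. Pairs .10/.90 and .30/.70 give 25.8 and 74.4. A score-type formula at .20/.80 gives 27.5.

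The .20/.80 Wald result is close but not exact, so the source of 36 stays open.

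**Step 3: check Table 1's effect size.** The SAP introduces the column as the R² of the regression. For a total R², the standard f² for one added predictor is c/(1 − R²).

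| R² | c | Printed f² | Printed N | c/(1 − R²) | N for 80% power (60–95%) |
|---|---|---|---|---|---|
| .30 | .02 | .071 | 112 | .029 | 277 (174–457) |
| .30 | .05 | .200 | 42 | .071 | 112 (71–184) |
| .30 | .10 | .500 | 19 | .143 | 58 (37–94) |
| .40 | .02 | .053 | 152 | .033 | 238 (149–392) |
| .40 | .05 | .143 | 58 | .083 | 97 (61–158) |
| .40 | .10 | .333 | 27 | .167 | 50 (32–81) |
| .50 | .02 | .042 | 191 | .040 | 199 (125–327) |
| .50 | .05 | .111 | 73 | .100 | 81 (52–132) |
| .50 | .10 | .250 | 34 | .200 | 42 (28–68) |

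The printed N also moves the wrong way. At c = .02 it rises with R² (112, 152, 191), although more explained variance leaves less residual variance and should lower N (277, 238, 199).

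Two other readings of the column are possible:
- If it is the share of variance *not* explained by the other predictors, the printed values are right.
- If it is the R² of the other predictors, f² = c/(1 − R² − c), and the .30 rows need 269, 105 and 50.

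**Step 4: what 120 covers (standard f², R² = .30).**
- Power at 120 is 45%, 83% and 98% for c = .02, .05 and .10.
- The f² with 80% power at 120 is .0665, so the smallest detectable c is .0665 × .70 = .047.
- At c = .05 the margin is (120 − 112)/120 = 6.7%. Assumed losses of 10% (108 left) and 20% (96 left) give 79% and 74% power.
- 120 covers seven of nine rows as printed, and six of nine with the standard f²; all three .02 rows fail.

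**The case against.** The strongest reply is that the SAP never says 36 comes from Table 1. The conclusion follows directly on sentences about a second table and about logistic regression, and a Wald logistic calculation at the stated R² of .30 comes close (36.5). On that view the figure is unsourced, not contradicted. This stands in part: a logistic source cannot be excluded, and the contradiction is limited to continuous outcomes. It does not rescue the sentence, which is worded in terms of treatment's contribution to R² and gives no outcome type, p1/p2 pair or unit. Nor does 36 fit the remark that dichotomous outcomes need slightly more participants: it is below two of the three R² = .30 rows (112 and 42) and nearly double the third (19).

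Second, the effect-size criticism depends on what the R² column means, and the margin at c = .05 moves with it: 6.7% if N = 112, 12.5% if N = 105, 65% if N = 42 as printed. That is fair, and it is why relabelling is offered as an alternative below. The SAP's own description of the column points to total R², which is the reading used for the main figures.

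Third, the consequence is modest. This is a Phase I feasibility study, 120 covers every R² = .30 row as printed, and the Protocol provides for extra recruitment if attrition is high. All true, but that provision does not say which effect 120 is meant to detect. The 70% and 40% margins are implications of the sentence, not claims the SAP makes.

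**Conclusion.** The concern holds. For continuous outcomes the concluding figure is not supported by Table 1, and its condition fixes no planning effect. On the standard f² at R² = .30, a total of 120 is adequate for contributions of about .047 or more before any loss. It tolerates 6.7% loss at .05 and has 45% power at .02. These figures rest on two-sided alpha .05, six predictors, and the R² column meaning total R². The enrolment target is not shown to be wrong; its justification is. This should be fixed, because the claim of adequate power and of room for attrition rests on that one sentence.

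**What to change.** 1. Correct Table 1's effect sizes and sample sizes to the standard f² (totals 277, 112, 58; 238, 97, 50; 199, 81, 42, with the ranges shown above). Alternatively, relabel the R² column to say what it measures, and recompute if it means the R² of the other predictors.
2. Replace 36 (23 to 59) and the bound of .30 with one named contribution and its row. If 36 has another source, state it: supply Table 2, the outcome type, the p1/p2 pair and the R² of the other predictors. A logistic figure should be labelled as such and not tied to a contribution to R².
3. State alpha and sidedness, and that N is the total across both arms.
4. Limit the adequacy claim to the contributions that 120, less a stated attrition rate, covers.

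A template, using .05 only as an example because the SAP names no target: *For continuous outcomes at R² = .30 and a treatment contribution of .05 (f² = .071, two-sided alpha .05, six predictors), 112 participants in total across both arms give 80% power (71 to 184 for power .60 to .95). The planned 120 allows 6.7% loss. A contribution of .02 (277 in total) is not covered.*

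The cost is a few SAP sentences and the computed columns of Table 1. The stated margin becomes less favourable; enrolment does not change.

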#### Statistical methods for outcome measures

A repeated measures ANOVA of pre- to posttest scores by condition will assess program effects. Multiple linear regression with continuous outcomes and logistic regression with dichotomous outcomes will also assess program effects. The regression models will use forward inclusion to enter (in order) pretest scores, additional baseline and demographic controls and specified interaction terms, and then model program effects on the four designated outcomes (knowledge, attitudes and beliefs, self-efficacy, and intentions).

